11.2 Potential Benefits

The INTERVENE-HF study may offer no benefit. Potential benefits of participating in the INTERVENE-HF study include having the OptiVol alert turned on and monitored remotely. This remote intrathoracic impedance monitoring, partnered with the external diagnostic information for risk stratification, may provide more individualized medication intervention that could lead to improved Heart Failure management.

The information gained from this study could result in the improved management of other Heart Failure study specific information. Additionally, information collected from this study may assist in the design of new product(s)/therapy(ies) and/or instructions for use.

11.3 Additional Considerations

The INTERVENE-HF study does not require exclusion of any aspects of standard of care in managing heart failure (HF) patients. Thus, physicians and nurses at a participating center can continue to manage their patients as per their clinic's standard of care practices. The INTERVENE-HF study provides additional opportunity for care interventions including use of PRN medications as per physician's standing orders (required) and reminders for assessment and adjustment to baseline medications (medication change or rationale for not changing medication required). These differences (between the standard of care for the subject as compared to the care provided to the subject when participating in the study) are described in further detail in the Patient Informed Consent (PIC) Template.

12 PLANNED STUDY CLOSURE, EARLY TERMINATION OF STUDY OR STUDY SUSPENSION

12.1 Planned study closure

Study Closure is a process initiated by distribution of a study closure letter. Study closure is defined as closure of a clinical study that occurs when Medtronic and/or regulatory requirements have been satisfied per the Clinical Investigation Plan and/or by a decision by Medtronic or regulatory authority), whichever occurs first. The study closure process is complete upon distribution of the Final Report or after final payments, whichever occurs last. Ongoing IRB oversight is required until the overall study closure process is complete. Refer to section 7.14 for additional information regarding study exit procedures.

12.2 Early termination or suspension

Early Termination of the Study is the closure of a clinical study that occurs prior to meeting defined endpoints. This is possible for the whole study or a single center. Study Suspension is a temporary postponement of study activities related to enrollment and distribution of the product. This is possible for the whole study or a single center.

12.2.1 Study-wide termination or suspension

Possible reasons for considering study suspension or termination of the study include but are not limited to:

- Adverse events associated with the system or product under investigation which might endanger the safety or welfare of the subject
- Observed/suspected performance different from the product's design intent
- Decision by Medtronic or regulatory body (where the study is operating under regulatory body authority)
- Technical issues during the manufacturing process

12.2.2 Investigator/center termination or suspension

Possible reasons for clinical investigator or center termination or suspension include but are not limited to:

- Failure to obtain initial IRB approval or annual renewal of the study
- Persistent non-compliance to the clinical investigation (e.g. failure to adhere to inclusion/exclusion criteria, failure to follow subjects per scheduled follow-ups)
- Lack of enrollment
- Noncompliance to regulations and the terms of the Clinical Trial Agreement (e.g. failure to submit data in a timely manner, failure to follow-up on data queries and monitoring findings in a timely manner, etc.)
- IRB suspension of the center
- Fraud or fraudulent misconduct is discovered (as defined by local law and regulations)
- Investigator request (e.g. no longer able to support the study)

12.3 Procedures for termination or suspension

12.3.1 Medtronic-initiated and regulatory authority-initiated

- Medtronic will promptly inform the clinical investigators of the termination or suspension and the reasons and inform the regulatory authority(ies) where required
- In the case of study termination or suspension for reasons other than a temporary IRB approval lapse, the investigator will promptly inform the IRB
- In the case of study termination, the investigator must inform the subjects and may inform the personal physician of the subjects to ensure appropriate care and follow-up is provided
- In the case of a study suspension, subject enrollment must stop until the suspension is lifted by Medtronic
- In the case of a study suspension, enrolled subjects should continue to be followed out of consideration of their safety, rights and welfare

12.3.2 Investigator-initiated

- The investigator will inform Medtronic and provide a detailed written explanation of the termination or suspension
- The investigator will promptly inform the institution (where required per regulatory requirements)
- The investigator will promptly inform the IRB
- The investigator will promptly inform the subjects and/or the personal physician of the subjects to ensure appropriate care and follow-up is provided

- In the case of a study suspension, subjects enrolled should continue to be followed out of consideration of their safety, rights and welfare

12.3.3 IRB-initiated

- The investigator will inform Medtronic and provide a detailed written explanation of the termination or suspension within 5 business days
- Subject enrollment must stop until the suspension is lifted
- Subjects already enrolled should continue to be followed in accordance with IRB policy or its determination that an overriding safety concern or ethical issue is involved
- The investigator will inform his/her institution (where required per local requirements)
- The investigator will promptly inform the subjects, or legally-authorized designees or guardians and/or the personal physician of the subjects, with the rationale for the study termination or suspension

13 STATISTICAL METHODS AND DATA ANALYSIS

13.1 Sample size determination

INTERVENE-HF is a feasibility study to evaluate the system that combines integrated device diagnostics based risk stratification algorithm with a guided work flow process managed by a centralized communication center to manage HF patients. This system, for purposes of defining study objectives, will be termed the “Integrated Diagnostics Medication Intervention Strategy.” Findings from this feasibility study will be used to guide subsequent planning of a pivotal study.

As a feasibility trial, the INTERVENE-HF study is not designed to be powered for specific endpoints. However, the sample size for this study was chosen with the goal of gaining a first time experience with the Integrated Diagnostic Medication Intervention Strategy in a broad number of patients to understand the safety, effectiveness and potential patient benefit of the strategy.

The study plans to enroll up to 400 subjects to yield up to 200 eligible subjects that meet screening criteria from 20 centers in the US with follow up for at least 12 months. The study is estimated to be completed in approximately 30 months including 18 months of enrollment and 12 months of follow-up from the last enrolled subject. The objectives of the study focus on the effectiveness and safety of the Integrated Diagnostics Medication Intervention Strategy. Interim analyses of these objectives will take place and if data are deemed to sufficiently characterize the study objectives by the sponsor at one of these analyses, enrollment and/or follow-up will be stopped. In addition, in order to have an early check on the subjects’ safety, a preliminary safety interim data analysis will take place after 10 PRN interventions have been implemented and the last PRN intervention has been followed up for 14 days.

The unpublished data of a Medtronic sponsored study (OptiLink HF) shows that among the subjects who had had CRT-D implanted for at least nine months and had NYHA class II or III nine months post implantation, 58% had at least one OptiVol crossing within the next 12 months of follow-up (of which 39%, 28%, 19%, 9% and 5% had one, two, three, four and more than four OptiVol crossings, respectively). Furthermore, about two-thirds of the subjects in that study had OptiVol version 1 and the rest had OptiVol version 2 and it is known that OptiVol version 2 generates fewer alerts. Therefore, we assume in the INTERVENE-HF study that:

- (1) 55% of the enrolled subjects who meet screening criteria and complete the baseline and programming visit will have at least one OptiVol crossing within the 12 months of follow-up; and
- (2) The distribution for those experiencing OptiVol crossings during the 12 months of follow up is the same as the results from the unpublished data.

As shown in Table 18, this leads to approximately 233 OptiVol crossings in 110 subjects (55% of 200 subjects) to be observed in the INTERVENE-HF study. Furthermore, literature

has indicated that 45% of OptiVol crossings are HF related²⁰. This means about 105 out of the 233 OptiVol crossings would require PRN implementation in this study.

Table 18: Number of OptiVol crossings expected from 110 (55% of 200) subjects

Assumption		Estimation	
Crossing(s)	% of subjects having the crossing(s)	Expected # of subjects having the crossings	Expected # of crossings
1	39%	43	43*1=43
2	28%	31	31*2=62
3	19%	21	21*3=63
4	9%	10	10*4=40
>4	5%	5	5*5=25
Total		110	233

13.2 General considerations

Medtronic employees or designees will perform all statistical analyses.

A separate Statistical Analysis Plan (SAP) will be created and will include a comprehensive description of the statistical methods and analyses to be included in reports that include analysis of endpoints. Any change to the data analysis methods described in the CIP will require an amendment only if it changes a principal feature of the CIP. Any other change to the data analysis methods described in the CIP, and the justification for making the change, will be described in the clinical study report.

In addition, the SAP will further describe pre-specified data handling rules. Additional exploratory analyses of the data may be conducted as deemed appropriate.

All objectives will be analyzed once the last enrolled subject has completed the 12-month follow-up visit and/or during interim analyses (interim analyses performed after 100 and 150 subjects are enrolled and have completed the baseline and programming visit). The primary analysis for each objective will not account for missing data. If missing data is an issue, a sensitivity analysis will be performed accordingly. The analysis results will be included in the study report(s).

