1.2 Study Description

The INTERVENE-HF study is a prospective, non-randomized, multi-center (US only), investigational, feasibility study. Patients with heart failure that have an implanted commercially available Medtronic cardiac resynchronization therapy defibrillator (CRT-D) device will be enrolled in the study. The basic INTERVENE-HF research system is comprised of the pre-existing Medtronic, CRT-D device, investigational 2090 programmer software capable of turning ON/OFF the silent OptiVol[®] wireless CareAlert, and the INTERVENE Study Communication Center (ISCC). The ISCC will reside with the Care Management Service (formerly Cardiocom) business unit of Medtronic. The INTERVENE-HF study will have a dedicated team of licensed nurses at ISCC that will guide and monitor subjects through an individualized, physician prescribed medication intervention for diuretics and other acute volume management drugs after their silent OptiVol CareAlert has been transmitted and medication intervention is warranted.

The study is expected to be conducted at up to 20 centers located in the United States. Up to 400 subjects will be enrolled to yield up to 200 eligible subjects that meet screening criteria. This study will be conducted in subjects with an implanted, commercially available, Medtronic, CRT-D device. A detailed list of these devices and model numbers is provided in Table 4. To ensure a widespread distribution of data and minimize center bias in study results, the maximum number of subjects enrolled at a single center is 30 subjects. It is estimated that subject enrollment will take approximately 12 to 18 months. Each enrolled subject will be followed every 2 months from time of enrollment to end of the study. It is anticipated that subjects will participate in the study for a minimum duration of 12 months and up to approximately 30 months. The study will end after the last enrolled subject completes the 12-month follow-up. Because INTERVENE-HF is a feasibility study, it is not intended to show an outcome of improvement. Rather the objective is to test the operational feasibility and safety of device diagnostics *plus* an intervention system as set forth in the primary and secondary objectives. Interim analyses of these objectives will take place and if data are deemed to sufficiently characterize the study objectives by the sponsor at one of these analyses, enrollment and/or follow-up will be stopped.

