5. METHODOLOGY

5.1 Study objectives

INTERVENE-HF is a prospective, non-randomized, single-arm feasibility study to evaluate the system that combines integrated device diagnostics based risk stratification algorithm with a guided work flow process managed by a centralized communication center to manage HF patients. This system, for purposes of defining study objectives will be termed the “Integrated Diagnostics Medication Intervention Strategy”. Details of this system are available in Section 3. Findings from this feasibility study will be used to guide subsequent planning of a pivotal study.

As a feasibility trial, the INTERVENE-HF study is not designed to be powered for specific endpoints. Therefore, it does not require justification on sample size. The following two primary objectives are proposed to determine effectiveness and safety of the Integrated Diagnostics Medication Intervention Strategy. No secondary objectives are proposed. Additionally, one ancillary objective characterizing the occurrence of HF events in the study population will be assessed.

Primary Objectives:

1. To characterize the effectiveness of the Integrated Diagnostics Medication Intervention Strategy in resolving the subject risk.
2. To characterize the safety of the Integrated Diagnostics Medication Intervention Strategy in resolving the subject risk.

Ancillary Objectives:

1. To characterize the occurrence of HF events in the study subjects.

NOTE: Intervention for heart failure decompensation (HF event) is defined as an event requiring invasive intervention (i.e. IV diuretics, ultrafiltration, or equivalent) or inpatient hospitalization.

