13.3.2 Endpoint Definition

Once initiated, the Integrated Diagnostic Medication Intervention Strategy will be regarded as being effective if all the following criteria are met:

- The intrathoracic impedance of a subject recovers per defined criterion after completion of the Integrated Diagnostic Medication Intervention;
- The subject has no HF-related event (as adjudicated by the CEC) during or in the next 14 days after completion of the Integrated Diagnostic Medication Intervention;

NOTE: Intervention for heart failure decompensation (HF event) is defined as an event requiring invasive intervention (i.e. IV diuretics, ultrafiltration, or equivalent) or inpatient hospitalization.

- The subject has not experienced any adverse events that are related to the Integrated Diagnostic Medication Intervention per CEC adjudication and require medical care.

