13.3.7 Sample Size

As the above-mentioned, based on the experience from previous studies we expect to observe about 233 OptiVol crossings from 110 enrolled subjects in this trial and of them 105 OptiVol crossings would require Integrated Diagnostic Medication Intervention. There are no data to help us predict the percentage of OptiVol crossings receiving Integrated Diagnostic Medication Intervention or the effectiveness rate of Integrated Diagnostic Medication Intervention Strategy. We consider different scenarios in Table 19 and Figure 9 to estimate the precision on measuring the effectiveness rate of Integrated Diagnostic Medication Intervention Strategy.

The width of 95% CI for the effectiveness rate represents the measurement precision. Using the first row in Table 19 as an example, a total of 70 independent episodes with Integrated Diagnostic Medication Intervention produces a two-sided 95% CI with an actual width of 0.225 when the observed proportion of having effective treatment among those episodes is 0.7. This is based on the exact Clopper-Pearson confidence interval for one proportion assuming independent effectiveness status of Integrated Diagnostic Medication Intervention. Note that each episode is an OptiVol crossing that lead to the initiation of an Integrated Diagnostic Medication Intervention. Note also that for each scenario, we expect a narrower width (i.e. better precision) of 95% CI for the effectiveness rate in the framework of generalized linear model with GEE method. This is because GEE method takes the correlation among the effectiveness status of multiple episodes from the same subject into account, thus presumably results in a smaller standard error of the effectiveness rate.

Figure 9 is a visual illustration of Table 19.

Table 19: Table of the 95% Confidence Interval for 70-100 independent episodes

Confidence Level	Size (N)	Actual Width	Sample Proportion (P)	Lower Limit	Upper Limit
0.950	70	0.225	0.700	0.579	0.804
0.950	70	0.199	0.800	0.687	0.886
0.950	70	0.154	0.900	0.805	0.959
0.950	80	0.210	0.700	0.587	0.797
0.950	80	0.186	0.800	0.696	0.881
0.950	80	0.143	0.900	0.812	0.956
0.950	90	0.198	0.700	0.594	0.792
0.950	90	0.174	0.800	0.702	0.877
0.950	90	0.135	0.900	0.819	0.953
0.950	100	0.187	0.700	0.600	0.788
0.950	100	0.165	0.800	0.708	0.873
0.950	100	0.127	0.900	0.824	0.951

[figure not shown]

Figure 9: Graph of the 95% Confidence Interval for 70 to 100 independent episodes

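### Do the two interim looks need an episode-based trigger and a definition of sufficient data before the sponsor may stop?

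*Protocol*

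**What the plan says.** The looks are defined by subjects. Protocol 13.2 has "interim analyses performed after 100 and 150 subjects are enrolled and have completed the baseline and programming visit", and SAP 7.1.3 and 7.8.1.1 repeat the same counts. Protocol 13.1 attaches a consequence: "if data are deemed to sufficiently characterize the study objectives by the sponsor at one of these analyses, enrollment and/or follow-up will be stopped". SAP 7.8.1 carries the clause over without adding a criterion, and SAP 7.8.1.1 applies the final-analysis methods at the looks.

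The endpoints are defined by episodes. Each intervention is scored effective or not, and safe or not, and is analysed with an intercept-only logit GEE (Protocol 13.3.5 and 13.4.5; SAP 7.9.1.4 and 7.9.2.4). Effectiveness also requires no HF event "during or in the next 14 days after completion of the Integrated Diagnostic Medication Intervention". The safety endpoint in Protocol 13.4.2 has no such window.

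On yield, Protocol 13.1 says "this leads to approximately 233 OptiVol crossings in 110 subjects", of which about 105 would need the intervention over 12 months per subject. On precision, Protocol 13.3.7 says "We consider different scenarios in Table 19 and Figure 9 to estimate the precision on measuring the effectiveness rate", and Table 19 runs from 70 to 100 episodes. On ambition, Protocol 5.1 says "As a feasibility trial, the INTERVENE-HF study is not designed to be powered for specific endpoints", and 13.3.3 and 13.4.3 set no performance requirement.

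**The concern.** A subject-count trigger says little about how many episodes have accrued. When the 100th or 150th subject is programmed, most subjects have been followed for only a few months, so the figure of 105 does not apply at that point. A reader who sees Table 19 may assume that a stop would rest on something like 70-100 episodes, when the open clause allows a stop on far fewer. There is no data monitoring committee (Protocol 14), and sponsor staff or designees run the analyses. The text is therefore the only advance statement of what would count as enough, and it leaves that to judgement.

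There is also a technical edge case. If every episode at a look has the same outcome, the log odds are infinite and the planned GEE interval is unusable. The SAP's logistic sensitivity analysis fails in the same way. The rates are meant to guide a pivotal study, so a very imprecise or degenerate estimate could matter there.

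**Working it through.** **Plan's own figures.** 0.55 × 200 = 110 subjects; 43 + 62 + 63 + 40 + 25 = 233 crossings; 0.45 × 233 = 104.85, or about 105. All twelve rows of Table 19 reproduce with exact Clopper-Pearson limits.

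**Inputs.**
- Episode rate: 233/200 × 0.45 = 0.524 per subject-year (Protocol 13.1).
- Accrual: "It is estimated that subject enrollment will take approximately 12 to 18 months" (Protocol 1.2), taken as uniform to 200 programmed subjects.
- Lag to evaluability for effectiveness: day 8 assessment (Protocol 6.4.1) plus 14 days = 22 days = 0.723 month.
- Assumed: constant rate, no attrition, independent episodes.

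**Formula.** With accrual over A months, the n-th subject is programmed at T = A × n/200. Evaluable subject-years at T are n(T − L)²/(2T)/12, where L is the lag in months.

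- Look 1, A = 12, T = 6: 100 × 5.277²/12/12 = 19.3 subject-years; × 0.524 = 10.1 episodes.
- Look 1, A = 18, T = 9: 100 × 8.277²/18/12 = 31.7; × 0.524 = 16.6.
- Look 2, A = 12, T = 9: 150 × 8.277²/18/12 = 47.6; × 0.524 = 24.9.
- Look 2, A = 18, T = 13.5: 150 × 12.777²/27/12 = 75.6; × 0.524 = 39.6.

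The safety endpoint has no 14-day wait. With a lag of 0 to 8 days the counts are about 12-20 and 28-44.

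**Exact 95% width near 70%, whole counts.**

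| Episodes | Width |
|---|---|
| 7/10 | 0.586 |
| 12/17 | 0.456 |
| 18/25 | 0.373 |
| 28/40 | 0.300 |
| 49/70 | 0.225 |

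**How firm the counts are.**
- Data cut 3 months after the trigger, accrual continuing: 25-31 and 46-60 evaluable.
- Cumulative accrual shaped as t^0.5 to t² (20-day lag): about 6-17 and 19-40.
- Every crossing treated, not 45%: about 23-38 and 55-90.
- Enrichment: Protocol 5.2.1 admits subjects through a recent crossing. If 70-80% rather than 55% had a crossing (an assumption), scaling by 70/55 to 80/55 gives about 13-24 and 32-58.

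**If the study is not cut short.** Mean follow-up is 12 + A/2 months, so 200 subjects give 300-350 subject-years. Removing the lag (200 × 0.723/12 = 12.0) and multiplying by 0.524 gives 151-177 evaluable episodes.

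**If only enrolment stops and 12 months' follow-up is kept.** From look 1, 125 to 137.5 subject-years less 6.0, × 0.524, gives 62-69. From look 2, 206.25 to 234.4 less 9.0, × 0.524, gives 103-118. Small counts are therefore mainly a matter of stopping follow-up.

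**Edge case.** At Table 19's illustrative rate of 0.9, the chance that all effectiveness-evaluable episodes succeed is 0.9^17 = 0.17 to 0.9^10 = 0.35 at look 1, and 0.9^40 = 0.015 to 0.9^25 = 0.07 at look 2. On the safety counts it is 0.9^20 = 0.12 to 0.9^12 = 0.28, and 0.9^44 = 0.01 to 0.9^28 = 0.05. The exact interval stays usable: its lower limit is 0.025^(1/10) = 0.692 for 10/10 and 0.025^(1/17) = 0.805 for 17/17.

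**The case for a change.** The best case for a change is that feasibility status excuses the lack of a power target but not an undefined stopping phrase. The plan shows that it can use an episode trigger: the preliminary safety analysis waits for 10 interventions plus 14 days. Fixing sufficiency in advance as a count, whatever the observed rates, would cost only wording and would prevent any suspicion that a stop followed a favourable result.

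Part of this stands. The phrase is undefined, the expected counts are not stated, and a stop prompted by a good-looking rate would flatter the estimate. But the clause concerns how well the objectives are characterised, not whether a result is good, and no success claim depends on it. A count chosen by the sponsor would bind little, because Protocol 12.2.1 separately lets the sponsor end the study. A count near 70 is expected only at about month 15 to 18, so a follow-up stop would need an added look and longer follow-up. That is a debatable trade-off in a study with no precision target.

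The edge case is real but visible, since no analyst would report infinite log odds. The exact interval is already the method behind Table 19, the SAP introduction says the plan does not limit the analyses, and Protocol 13.2 lets non-principal method changes be described in the study report.

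**Conclusion.** No change is needed. On the trigger dates the plan's rates imply about 10-17 and 25-40 effectiveness-evaluable episodes (about 12-20 and 28-44 for safety), and exact widths at about 70% of 0.59-0.46 and 0.37-0.30. These figures rest on uniform 12- to 18-month accrual, a constant rate, no attrition and independent episodes. They move with the data cut, accrual shape and uptake, and the second look could exceed 70 if every crossing were treated.

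The numbers fall below Table 19's range, but that table is a set of scenarios and not a target. With no hypothesis, power, performance or precision requirement, nothing stated is breached. Early intervals would be wide but interpretable, and their width would be plain to the planners of a pivotal study. Leaving the stop to sponsor judgement is a fair choice for a feasibility study. The data cut, the evaluable count at each look and an exact interval when all outcomes agree are details that a competent interim report supplies.
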